3.2.1 Dose-Limiting Toxicity

Determination of DLTs will be made during the first 21 days of combination treatment with rociletinib and MPDL3280A (ie, during Cycle 1 after the rociletinib Run-in-Period) in the Dose Finding Phase. A DLT is defined as a clinically significant AE or laboratory abnormality assessed as at least related to the study drug (rociletinib and/or MPDL3280A), unrelated to disease progression, and that meets any of the following criteria:

Cytopenia:

- Grade 4 neutropenia persisting for more than 7 days;
- Febrile neutropenia, defined as an absolute neutrophil count (ANC) < 1000/mm³ and a single temperature of > 38.3°C (101°F);
- Grade 4 thrombocytopenia persisting for more than 7 days or thrombocytopenia with clinically significant bleeding (ie, bleeding that requires blood or platelet transfusion or other medical intervention, or that may cause disability or death, such as cerebral hemorrhage).

Organ Toxicity:

• Grade \geq 3 symptomatic hepatic toxicities lasting for > 48 hours, or Grade \geq 3 asymptomatic hepatic toxicities lasting for > 7 days with the following exception:

- For patients with Grade 2 Alkaline phosphatase (ALP) abnormality at baseline, an increase to > 8 × the upper limit of normal (ULN) lasting > 48 hours (if symptomatic) or > 7 days (if asymptomatic) will be considered a DLT.
- Grade \geq 3 nonhematologic, nonhepatic organ toxicity, with the following exceptions:
 - **DLT Toxicity Exceptions**
 - Grade 3 nausea, vomiting, or diarrhea that resolves to Grade ≤ 1 within 7 days after starting appropriate supportive therapy (see Section 6.2.2);
 - Grade ≥ 3 asymptomatic or mildly symptomatic rash that can be adequately managed with supportive care (see Section 6.2.4) or symptomatic rash that resolves to become asymptomatic and/or Grade ≤ 2 within 7 days of appropriate supportive therapy;
 - Grade \geq 3 fatigue that resolves to Grade \leq 2 within 7 days;
 - Grade 3 arthralgia that can be adequately managed with supportive care or that resolves to Grade ≤ 2 within 7 days;
 - Grade 3 autoimmune thyroiditis or other endocrine abnormality that can be managed by endocrine therapy and that would not necessitate initiation of systemic corticosteroids;
 - Grade 3 fever (in the absence of any clinically significant source of fever) that resolves to Grade ≤ 2 within 7 days with supportive care;
 - Grade 3 laboratory abnormality that is asymptomatic and deemed by the Investigator to be not clinically significant;

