6.2.3 Management of Hepatotoxicity

Immune-mediated hepatitis has been associated with the administration of MPDL3280A. Eligible patients must have adequate liver function, as manifested by measurements of total bilirubin and hepatic transaminase, and liver function will be monitored throughout study treatment.

While on this study, patients presenting with right upper-quadrant abdominal pain and/or unexplained nausea or vomiting should have LFTs performed immediately and reviewed before administration of the next dose of study drug.

If LFTs increase, neoplastic, concurrent medications, viral hepatitis, and toxic etiologies should be considered and addressed, as appropriate. Imaging of the liver, gall bladder and biliary tree should be performed to rule out neoplastic or other causes for increased LFTs. Anti-nuclear antibody, perinuclear anti-neutrophil cytoplasmic antibody, anti-liver kidney microsomal antibodies, and anti-smooth muscle antibody tests should be performed if an autoimmune etiology is considered.

Patients with LFT abnormalities should be managed according to Table 13.

Description	Management
AST/ALT (> ULN to 3 × ULN) with total bilirubin < 2 × ULN	• Continue with the standard monitoring plan (ie, LFTs every 3 weeks before dosing).
AST/ALT (> 3 × ULN to < 10 × ULN) with total bilirubin < 2 × ULN	• Continue MPDL3280A. Monitor LFTs at least weekly. Consider referral to a hepatologist.
$AST/ALT > 10 \times ULN$	• Hold MPDL3280A;
	• Consider administering IV steroids for 24-48 hours (prednisone 60 mg/day equivalent) followed by oral prednisone (or equivalent) taper over 2-4 weeks;
	 If LFT results do not decrease within 48 hours after initiation of systemic steroids, addition of an alternative immunosuppressive agent (eg, mycophenolate or TNF-α antagonist) to the corticosteroid regimen may be considered;
	• Monitor LFTs every 48-72 hours until decreasing and then follow weekly;
	 Restart MPDL3280A after discussion with the Medical Monitor if AST/ALT ≤ 3 × ULN with bilirubin < 2 × ULN and steroid dose is ≤ 10 mg oral prednisone equivalent per day;
	• Permanently discontinue MPDL3280A for life-threatening immune- related hepatic events.

 Table 13:
 Management Guidelines for Hepatotoxicity (LFT Abnormalities)

Table 13: Management Guidelines for Hepatotoxicity (co	continued)	
--	------------	--

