6.2.4 Management of Dermatologic Toxicity

Treatment-emergent rash (eg, maculopapular or purpura) has been associated with MPDL3280A. The majority of cases of rash were mild in severity and self-limited, with or without pruritus.

A dermatologist should evaluate persistent and/or severe rash or pruritus. A biopsy should be considered unless contraindicated. Dermatologic toxicity and rash should be managed according to Table 14.

Description	Management
Grade 1 mild < 10% BSA	 Continue MPDL3280A. Symptomatic therapy with antihistamine PRN; Consider topical steroids and/or other symptomatic therapy (eg, antihistamines).
Grade 2 moderate 10%-30% BSA	 Continue MPDL3280A; Consider dermatologist referral; Administer topical steroids; Consider higher potency topical steroids if rash unresolved.
Grade 3 severe > 30% BSA	 Hold MPDL3280A; Consult dermatologist; Administer oral prednisone 10 mg or equivalent. If rash unresolved after 48-72 hours, administer oral prednisone 60 mg or equivalent; Restart MPDL3280A if rash resolved and systemic dose is ≤ 10 mg oral prednisone equivalent per day; Permanently discontinue MPDL3280A for life-threatening immune-related dermatologic toxicity.

Table 14:Management Guidelines for Rash

BSA, body surface area; PRN, as needed.

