6.3 Overlapping Expected or Potential Toxicities

Guidelines for the management of specific expected or potential overlapping toxicities for rociletinib and MPDL3280A are described in Table 18.

Table 18:Management of Overlapping Toxicities

Toxicity	Attribution to both agents
Rash/Skin Toxicity:	Grade 2: continue both agents; initiate supportive care.
	Grade 3:
	 Obtain dermatology consult;
	■ Hold rociletinib and MPDL3280A until resolved to ≤ Grade 1, then reinitiate rociletinib at a dose agreed upon with the Sponsor's Medical Monitor; (dose delays longer than 14 days also require discussion with the Medical Monitor);
	 Restart MPDL3280A if rash does not occur within 14 days of rociletinib re-initiation;
	 Hold rociletinib and permanently discontinue MPDL3280A if the patient experiences recurrent Grade ≥ 3 skin toxicity. When rash is Grade 1, restart rociletinib at previous dose. If Grade ≥ 3 rash recurs, rociletinib should be discontinued permanently.
	Grade 4 : Permanently discontinue MPDL3280A. Hold rociletinib until rash is Grade 1 and restart at one dose level lower (dose delays longer than 14 days require discussion with the Medical Monitor). If Grade \geq 3 rash recurs, rociletinib should
	be discontinued.
Diarrhea:	Grade 2 : Supportive care unless > 48 to 72 hrs. Then reduce dose of rociletinib and hold MPDL3280A until resolves to < Grade 1.
	Grade 3 : Hold rociletinib and MPDL3280A Obtain gastroenterology consult, discontinue NSAIDs or medications known to exacerbate colitis, Initiate steroid treatment. If resolves to < Grade 1, then restart rociletinib at next lower dose. If no recurrent symptoms, within 14 days resume MPDL3280A as long as steroid dose is ≤ 10 mg oral prednisone equivalent per day (dose delays longer than 14 days require discussion with the Medical Monitor).
	Grade 4 : MPDL3280A should be permanently discontinued. Hold rociletinib until diarrhea is Grade 1 and restart at one dose level lower. If Grade \geq 3 diarrhea recurs, rociletinib should be permanently discontinued (dose delays longer than 14 days require discussion with the Medical Monitor).
Nausea/Vomiting:	Grade1-2: Continue treatment. Begin maximum supportive care and adequate anti-emetic treatments (see Section 7.6.1 for guidance on avoiding QT-prolonging concomitant medication).
	Grade ≥ 3:

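### The rash exception to the DLT definition has no upper grade, so a Grade 4 rash that settles within 7 days is not a DLT even where the management tables permanently stop MPDL3280A for it

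*Combined protocol and SAP*

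**What the plan says.** Section 3.2.1 makes any Grade 3 or higher nonhematologic, nonhepatic organ toxicity related to study drug in Cycle 1 a DLT, subject to a list of exceptions. The rash exception has two limbs. The first is "Grade ≥ 3 asymptomatic or mildly symptomatic rash that can be adequately managed with supportive care", with a pointer to Section 6.2.4. The second is "symptomatic rash that resolves to become asymptomatic and/or Grade ≤ 2 within 7 days of appropriate supportive therapy". Neither has an upper grade. The gastrointestinal exception does: "Grade 3 nausea, vomiting, or diarrhea that resolves to Grade ≤ 1 within 7 days after starting appropriate supportive therapy".

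The management rules treat a Grade 4 rash as follows.

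- Section 6.3, Table 18, in a column for toxicity attributed to both agents: "Permanently discontinue MPDL3280A. Hold rociletinib until rash is Grade 1 and restart at one dose level lower".
- Section 6.2.4, Table 14, for rash managed as MPDL3280A toxicity: the rows end at Grade 3, with the added instruction "Permanently discontinue MPDL3280A for life-threatening immune-related dermatologic toxicity".
- Section 6.3, Table 18, Grade 4 diarrhea: "MPDL3280A should be permanently discontinued. Hold rociletinib until diarrhea is Grade 1 and restart at one dose level lower".

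Section 5.7.3 and Table 8 allow a rociletinib reduction in Cycle 1 only for a DLT or by CSC decision. Section 5.7.3 makes a patient evaluable with at least 75% of the planned dose of each drug, or with a DLT.

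**The concern.** The mTPI table in Appendix H works on the number of DLTs at the current dose. An event for which the protocol permanently withdraws one of the two drugs under test would ordinarily count as limiting the combination. Here it need not, and nothing elsewhere in the protocol puts it back: no rule says that permanent discontinuation of a study drug is itself a DLT.

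Two further mismatches follow. Table 18 calls for a lower rociletinib dose, while Section 5.7.3 forbids one in Cycle 1 unless there is a DLT or the CSC so decides. Evaluability also becomes unclear. Rociletinib is held until the rash is Grade 1, and 25% of 21 days is 5.25 days, so a longer hold leaves the patient below 75% of planned dose. Without DLT status that patient fails the Section 5.7.3 test, yet Section 3.2.2 replaces only patients who fell short for reasons other than drug-related AEs. At stake is whether 500 mg BID is accepted as the Phase 2 dose on an incomplete DLT count.

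**Working it through.** **Reading the text.** A Grade 4 rash meets the base rule. The second limb then removes it if it becomes asymptomatic or falls to Grade 2 or below within 7 days of supportive therapy. For diarrhea the Table 18 action is the same, but the exception stops at Grade 3, so Grade 4 diarrhea remains a DLT.

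**Other uncapped exceptions.** Fatigue, hyperglycemia and creatine kinase also start at Grade 3 with no cap. None ends the combination at a first Grade 4 event. Table 10 lets rociletinib restart at the same dose after Grade 4 hyperglycemia. Fatigue and creatine kinase fall under the last general row of Table 18, where MPDL3280A resumes after a first event.

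**Reproducing Appendix H.** Inputs from Appendix H: target 33%, equivalence interval 28% to 38%, and the 95% limit of its safety rules, used here for U. Assumed: a Beta(1,1) prior. With x DLTs in n patients, the posterior is Beta(1+x, 1+n−x). The decision is the interval with the largest posterior probability per unit length, and U is added when P(p > 0.33) > 0.95.

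| x/n | E | S | D | P(p > 0.33) | Decision |
|---|---|---|---|---|---|
| 0/3 | 2.61 | 1.21 | 0.24 | 0.20 | E |
| 1/3 | 1.12 | 1.77 | 0.82 | 0.60 | S |
| 2/3 | 0.25 | 0.88 | 1.36 | 0.89 | D |
| 3/3 | 0.02 | 0.15 | 1.58 | 0.99 | DU |
| 3/6 | 0.36 | 1.51 | 1.21 | 0.83 | S |
| 4/6 | 0.08 | 0.57 | 1.49 | 0.957 | DU |

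All six match the printed table, as do the 91 cells checked in total (0 to 7 DLTs, up to 14 patients).

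**One uncounted rash among the first 3 at 500 mg.** Let p be the rate of other DLTs (assumed).

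- One of the other two has a DLT, so 2/3 (D) is read as 1/3 (S): 2p(1−p).
- Both have a DLT, so 3/3 (DU) is read as 2/3 (D): p².
- Sum: 1 − (1−p)².

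| p | D read as S | DU read as D | Either |
|---|---|---|---|
| 10% | 18% | 1% | 19% |
| 20% | 32% | 4% | 36% |
| 33% | 44% | 11% | 55% |

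The change from 1/3 (S) to 0/3 (E) has no effect at 500 mg, where no higher dose is planned. In Cohort −1 (375 mg) it would point back to 500 mg unless 500 mg had been marked U.

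**One uncounted rash among 6.** The change is 4/6 (DU) read as 3/6 (S), so 3 of the other 5 must have DLTs. Section 3.2.2 requires a CSC review after 3 evaluable patients, so the sixth patient is reached only if at most 1 DLT was counted there. Let q = 1−p, with the rash equally likely in either half.

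- Rash in the first 3: the joint probability of passing and ending at 3/6 is q²·p³ + 2pq·3p²q = 7p³q². The chance of passing is 1 − p².
- Rash in the last 3: the joint probability is 3pq²·p² = 3p³q². The chance of passing is q³ + 3pq².
- Given that 6 are reached: ½(7+3)p³q² ÷ ½(1 − p² + q³ + 3pq²).

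For p = 10%, 20% and 33% this is 0.00405/0.981 = 0.4%, 0.0256/0.928 = 2.8% and 0.0807/0.818 = 9.9%.

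**Unconditional scale, for illustration.** If a qualifying rash occurred in 0.5% to 2% of patients (assumed), the chance of at least one among 3 is 1 − 0.995³ = 1.5% to 1 − 0.98³ = 5.9%. Multiplying by 0.19 and 0.55 gives about 0.3% to 3.2% for a changed 3-patient decision.

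**The case against.** **Deliberate tolerance of short events.** Brief Grade 4 toxicity is excused elsewhere: neutropenia up to 7 days, and hyperglycemia explicitly above Grade 3. A DLT and an individual stopping rule also serve different ends, because cohort decisions can change only rociletinib. This explains the style of the list. It does not explain why rash is treated differently from diarrhea, when Table 18 gives both the same action.

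**Doubtful reach.** A life-threatening rash would seldom be mildly symptomatic, so the first limb hardly matters. A rash that settles only after both drugs are withheld may not count as having settled on supportive therapy. Grade 4 rash also depends on CTCAE v4.03, which is not reproduced. These points narrow the gap, but no sentence closes it.

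**CSC oversight.** The mTPI table only guides. The CSC confirms DLTs, sees all safety data, may meet at any time, and must act before rociletinib is reduced in Cycle 1 without a DLT. This is a real safeguard and keeps the point small. But the committee is given no rule for counting an exempted event.

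**Stronger readings to avoid.** A reader might infer that every drug-related Grade 4 rash ends the combination. Table 18 applies only when both agents are blamed, and Table 14 only to life-threatening immune-related rash. Nor is the rociletinib reduction automatic in Cycle 1. A reader might also take 10p³q², which is 0.8%, 5.1% and 16.1%, as the 6-patient effect; that ignores the review after 3 patients.

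**Conclusion.** The gap is real on the wording: the DLT definition leaves out an event for which the protocol's own tables, under the attribution conditions above, permanently withdraw MPDL3280A. It is worth correcting because the correction is cheap, not because the effect is large.

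The frequency cannot be bounded from the documents. It is probably low: rash on rociletinib alone affected 6 patients (4%) and was mild (Section 1.3.1), and most MPDL3280A events were Grade 1 or 2, although rash is among those seen in at least 10% (Section 1.4.1). The 3-patient and 6-patient percentages are conditional on such a rash occurring. They also assume a rate for other DLTs, that the CSC follows the table, and that the rash patient stays in the denominator, which Sections 3.2.2 and 5.7.3 leave unclear. A reader might conclude that the trial is likely to carry too toxic a dose into Phase 2; the documents do not support that.

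**What to change.** In the rash bullet of Section 3.2.1, replace the opening Grade ≥ 3 of the first limb with Grade 3, and insert Grade 3 before "symptomatic rash that resolves to become asymptomatic and/or Grade ≤ 2 within 7 days of appropriate supportive therapy". Any drug-related Grade 4 rash in Cycle 1 is then a DLT, as Grade 4 diarrhea already is. The patient is evaluable under Section 5.7.3, and the Table 18 reduction is permitted in Cycle 1.

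This is one bullet in an amendment, with no change to sample size, assessments or Appendix H. The cost is an occasional extra DLT, and possibly a rociletinib de-escalation, for a quickly resolving rash that may be due to MPDL3280A.

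The edit does not reach the hepatic criterion, which has a similar feature: it counts "asymptomatic hepatic toxicities lasting for > 7 days" (48 hours if symptomatic), while Table 13 says "Permanently discontinue MPDL3280A for life-threatening immune- related hepatic events". Whether to align that as well is a separate decision.

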1.3.1 Safety of Rociletinib from Clinical Studies

Preliminary safety data are presented for the ongoing CO-1686-008 and completed CO-1686-016 studies. As of 04 June 2014, 190 patients have received at least one dose of rociletinib: 42 healthy male volunteers (Study CO-1686-016) and 148 patients with advanced NSCLC (Study CO-1686-008). The overall safety data presented here are for NSCLC patients who received rociletinib in Study CO-1686-008.

Study CO-1686-008

Preliminary safety data are reported for 148 patients with advanced NSCLC in this study, including 57 patients who were treated with rociletinib free base at total daily doses ranging from 150 mg up to 1800 mg (once daily [QD], BID, and three times daily [TID] dosing schedules) and 91 patients who were treated with rociletinib HBr at total daily doses ranging from 1000 mg to 2000 mg (500 mg BID, 625 mg BID, 750 mg BID and 1000 mg BID). Rociletinib HBr is being studied in ongoing clinical studies and will be used in this study (Section 5.1).

Dose-Limiting Toxicities: Enrollment of patients to the dose escalation phase was completed in February 2014 with a DLT rate of < 33% at all evaluated doses. The DLT evaluable population included all patients who had completed Cycle 1, and who were enrolled while the dose escalation part of the study was ongoing. The most frequently reported DLT was hyperglycemia/glucose tolerance impaired which occurred at a similar frequency (11% to 25%) across all rociletinib dose levels with the rociletinib HBr formulation (500 mg BID, 625 mg BID, 750 mg BID, and 1000 mg BID). Hyperglycemia can be effectively managed with the addition of anti-hyperglycemic therapy and/or dose reductions. Guidance for the management of hyperglycemia associated with rociletinib treatment is provided in Section 6.1.2.

Serious Adverse Events (SAEs) and Deaths: A total of 43 patients experienced at least one SAE, and among these, 17 patients (11.5%) had an SAE assessed as related to study drug. The most commonly reported treatment-related SAE was hyperglycemia (reported by 6% of patients). Four patients (3%) experienced an SAE of vomiting, and 3 patients (2%) experienced

an SAE of nausea. All other treatment-related SAEs occurred in 2 or fewer patients. Treatment-related SAEs are summarized in Table 3.

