3.1 Clinical Safety Committee

Throughout the study, oversight will be provided by the Clinical Safety Committee (CSC), comprised of all Principal Investigators, the Sponsor's Medical Monitor and the Sponsor's drug safety representative. The CSC will:

- Review and confirm all DLTs;
- Determine all cohort dose-escalation and de-escalation decisions (assignment of Dosing Cohorts) during the Dose Finding Phase (Phase 1);
- Determine the MAD or MTD and RP2D to extend into the Expansion Phase (Phase 2), based on available safety, tolerability, and PK data;
- Review safety data for all patients during Phase 1 and Phase 2.

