 - Grade ≥ 3 hyperglycemia lasting ≤ 7 days. Grade > 3 hyperglycemia will be considered a DLT only if it lasts for more than 7 days despite optimized antihyperglycemic treatment (eg, oral anti-hyperglycemic therapy);
 - Grade ≥ 3 elevation of serum creatine kinase (CK) level that is asymptomatic (ie, not accompanied by signs, symptoms, or other laboratory abnormalities associated with rhabdomyolysis or myocardial injury) that is deemed by the Investigator to be clinically insignificant and that returns to Grade ≤ 2 within 7 days.

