Guidelines for management of hyperglycemia, based on the results of laboratory FBG values and patient symptoms, are presented in Table 10. Sites are encouraged to follow these guidelines, although management of individual patients may be influenced by local practices and the treating physician's judgment.

FBG Result	Antihyperglycemic Intervention ^a	Rociletinib Dose Modification
Grade 2 (> 160 to 250 mg/dL; > 8.9 to 13.9 mmol/L)	• If asymptomatic, ^b repeat test within 1 week; if results in this range at least twice in 1 week, start antihyperglycemic ^c and continue home monitoring;	• Rociletinib may continue without interruption or dose reduction
	• If symptomatic, ^b start antihyperglycemic and continue home monitoring.	
Grade 3 (> 250 to 500 mg/dL;	• Start antihyperglycemic and continue home monitoring.	• If asymptomatic, ^b rociletinib may continue without interruption or dose reduction;
> 13.9 to 27.8 mmol/L)		• If symptomatic, ^b interrupt rociletinib until resolution/improvement in symptoms and FBG < 250 mg/dL (< 13.9 mmol/L) ^c .
Grade 4 (> 500 mg/dL; > 27.8 mmol/L)	 Start antihyperglycemic and continue home monitoring. Consider adding a second antihyperglycemic agent.^d 	 Interrupt rociletinib dosing until resolution/improvement in symptoms and FBG < 250 mg/dL (< 13.9 mmol/L).^c

Table 10: Management Guidelines for Hyperglycemia

FBG, fasting blood glucose

^a Oral antihyperglycemic agent (eg, metformin), which may need to be maintained for duration of rociletinib treatment. Use of insulin or agents which increase insulin production (eg, sulphonyl ureas) is generally not recommended because the mechanism of rociletinib-induced hyperglycemia is not due to a deficit in insulin production.

^b Increased nausea, vomiting, anorexia, diarrhea, and fatigue have been most common symptoms of hyperglycemia.

^c Per Investigator discretion, rociletinib may be restarted at the same dose. A reduced dose may also be considered if glucose levels prove difficult to control.

^d Additional antihyperglycemia agents such as SGLT2 inhibitors (eg, dapagliflozin) or pioglitazone, which increase glucose uptake or increase glucose excretion, may be added to metformin.

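### As printed, the hyperglycemia DLT exception sets its optimized-treatment test for Grade > 3 only, so a clinically significant event lasting over 7 days without optimized treatment is a DLT at Grade 3 but not at Grade 4

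*Combined protocol and SAP*

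**What the plan says.** Section 3.2.1 of the protocol defines a DLT as a clinically significant, drug-related event in the first 21 days of combination treatment that meets a listed criterion. The criterion that covers hyperglycemia is Grade ≥ 3 "nonhematologic, nonhepatic organ toxicity, with the following exceptions".

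The hyperglycemia exception has two sentences. The first exempts Grade ≥ 3 "hyperglycemia lasting ≤ 7 days". The second reads: "Grade > 3 hyperglycemia will be considered a DLT only if it lasts for more than 7 days despite optimized antihyperglycemic treatment". Oral therapy is given as an example of such treatment.

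A separate exception covers a Grade 3 "laboratory abnormality that is asymptomatic and deemed by the Investigator to be not clinically significant". Another covers Grade 3 endocrine abnormalities that endocrine therapy can manage without systemic corticosteroids. Nothing elsewhere in the protocol restates the hyperglycemia threshold.

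**The concern.** The first sentence and the default rule both start at Grade 3. The second, as printed, starts above Grade 3. Only the second sentence asks whether treatment was optimized, so that question is put for Grade 4 and not for Grade 3. Where it decides the outcome, the milder event counts as a DLT and the more severe one does not. No clinical reason for this is given.

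The definition is used in three places. DLTs are a Phase 1 primary endpoint. Their count is the input to the mTPI table in Appendix H. Under Section 5.7.4, a rociletinib-related toxicity equivalent to a DLT calls for a hold and a dose reduction, from Cycle 2 in Phase 1 and in every cycle of Phase 2. Hyperglycemia is also the exception most likely to be used: Section 1.3.1 reports it as the most frequent DLT with rociletinib alone, at 11% to 25% across the HBr dose levels.

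**Working it through.** **Step 1. Apply the rule as printed.** Take a clinically significant, drug-related event that no other Grade 3 exception covers.

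| Duration | Optimized treatment | Grade 3 | Grade 4 |
|---|---|---|---|
| ≤ 7 days | yes | not DLT | not DLT |
| ≤ 7 days | no | not DLT | not DLT |
| > 7 days | yes | DLT | DLT |
| > 7 days | no | **DLT** | **not DLT** |

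In the last row, Grade 3 fails the first sentence on duration and is outside the second, so the default makes it a DLT. Grade 4 is inside the second sentence and fails its treatment condition, so it is not a DLT.

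**Step 2. Repeat with Grade ≥ 3 in the second sentence.** The last row becomes not DLT at both grades, and the other three rows do not change. The correction therefore alters one cell: Grade 3, more than 7 days, treatment not optimized. It turns a DLT into a non-DLT. No Grade 4 cell moves.

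**Step 3. See what one such patient does in Appendix H.** The inputs are the target of 33% and the equivalence interval of 28% to 38% from Appendix H. A Beta(1,1) prior is assumed, because the appendix does not print one. With x DLTs in n patients the posterior is Beta(1 + x, 1 + n − x), with distribution function F. The score of each decision is its posterior probability divided by the width of its interval:

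- E: F(0.28)/0.28
- S: [F(0.38) − F(0.28)]/0.10
- D: [1 − F(0.38)]/0.62

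The highest score wins. U is added if P(rate > 0.33) exceeds 0.95, the limit in the appendix's safety rules.

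| DLTs/n | E | S | D | P(rate > 0.33) | Recomputed | Printed table |
|---|---|---|---|---|---|---|
| 1/3 | 1.119 | 1.768 | 0.823 | 0.599 | S | S |
| 2/3 | 0.248 | 0.876 | 1.360 | 0.892 | D | D |
| 3/6 | 0.363 | 1.505 | 1.206 | 0.832 | S | S |
| 4/6 | 0.076 | 0.569 | 1.487 | 0.957 | DU | DU |
| 4/9 | 0.422 | 1.996 | 1.101 | 0.794 | S | S |
| 5/9 | 0.122 | 1.006 | 1.396 | 0.927 | D | D |

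For example, at 2/3 the D score is 0.8431/0.62 = 1.360 and the S score is 0.0876/0.10 = 0.876.

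The recomputed decisions match the printed table. If one of the counted patients sits in the disputed cell, the correction moves 2/3 to 1/3 (D to S), 4/6 to 3/6 (DU to S) or 5/9 to 4/9 (D to S). In the first cohort of Table 5, that is the difference between dropping rociletinib from 500 mg to 375 mg BID and staying at 500 mg BID.

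**Step 4. Ask how often the cell could occur.** The documents do not say. The 11% to 25% in Section 1.3.1 covers hyperglycemia DLTs of every kind, in a study whose DLT definition is not given. No rate for the disputed cell follows from it.

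**The case against.** **The symbol may not be in the source.** The point rests on > against ≥, and the text was machine-read from a PDF. The same reading gives the spacing of ECG tracings in Table 1, footnote T, as more than 2 minutes in some copies of that footnote and at least 2 minutes in another. It also gives the Day 1 omission window as under 3 days in Table 1, footnote B, and as at most 3 days in Section 8.1. In the other direction, ≥ and ≤ were both read in the sentence just before the disputed one. The documents cannot settle the matter, so this objection stands and lowers the confidence.

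**Another exception may cover Grade 3.** Hyperglycemia could be read as an endocrine abnormality: Section 9.6 lists diabetes mellitus among the endocrinopathies. If that exception applied, Grade 3 would not be a DLT either and the difference would vanish. This is the weaker reading. Hyperglycemia has its own exception, and Tables 3 and 4 place it under metabolism and nutrition disorders. The laboratory exception does not help, because it covers only events judged not clinically significant.

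**Practice should keep the cell rare.** This largely stands. Fasting glucose is scheduled on Days 1, 4, 8 and 15 of Cycle 1. Table 10 starts an antihyperglycemic at Grade 3 even without symptoms, and at Grade 4 it adds: "Interrupt rociletinib dosing until" symptoms and glucose improve. The run-in keeps patients who need a rociletinib reduction, or a delay of more than 48 hours, off the combination. The Clinical Safety Committee is to "Review and confirm all DLTs", and the mTPI table only guides its decisions. However, Table 10 is advisory ("Sites are encouraged to follow these guidelines") and lets asymptomatic Grade 3 continue without interruption. The committee still needs a clear definition to confirm against.

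**A reader might infer that Grade 4 events escape the DLT count.** The documents do not support that as an effect of the mismatch. Prolonged Grade 4 hyperglycemia without optimized treatment is not a DLT under either symbol. The printed wording errs only towards counting more.

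**Conclusion.** As printed, Section 3.2.1 treats Grade 3 more strictly than Grade 4 in one of four duration-by-treatment cells. Against a consistent rule it can only add a Grade 3 DLT, so any error is in the cautious direction: an unneeded step from 500 mg to 375 mg BID, or an unneeded hold and reduction under Section 5.7.4. One patient is enough to change an Appendix H entry, but the cell should be uncommon and its frequency cannot be estimated from the documents.

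The conclusion assumes that the source document has > in the second sentence, that the event is clinically significant, and that the endocrine exception does not extend to hyperglycemia. The point is minor. Confidence is low, mainly because of the first assumption.

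**What to change.** Check the source document first. If its second sentence already has Grade ≥ 3, nothing needs to change. If it has Grade > 3, replace the symbol with ≥, so that hyperglycemia of either grade is a DLT only when it persists beyond 7 days under optimized treatment. A reference to Table 10 would help to say what optimized means. The cost is one symbol and an optional cross-reference, with no change to data collection, sample size or the mTPI table.
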